6 MW was developed to assess cardiopulmonary fitness in patients with lung and cardiac disease

(5), but has been used widely to assess disability in older adults (6) and is the most common metric used when seeking FDA approval for interventions to improve physical function. We have experience with this measure in heart failure patients (7).

Treatment phase

NMES will be carried out bilaterally on the quadriceps using a portable stimulator (EMPI Continuum). Two adhesive electrodes will be affixed to the anterior surface of each thigh: ~1 cm distal to the inguinal crease and ~5 cm proximal to the patella, just lateral to the midline of the thigh to assure that it does not interfere with incisions for vein harvest. Symmetrical, biphasic pulses (400 μ s duration at 25 Hz) will be used, with a duty cycle of 25% (10 s on, 30 s off). Patients will be trained to conduct NMES sessions and will select stimulation intensities sufficient to cause visible muscle contractions below their pain threshold. Training in the use of the NMES device will begin prior to day of discharge. . This training will consist of one session per day of ~15 min to familiarize the volunteer with the unit and the exercise/contraction stimulus. Upon discharge, NMES sessions will occur 5 d/wk once per day for 45 min per occasion (5 min low-intensity warm-up, 40 min higher-intensity stimulation) for 4 wks. This program is meant to mimic an aerobic-type exercise stimulus (8) and has been shown in heart failure patients to have functional benefits over a similar treatment period (9, 10). We acknowledge that the NMES training load is substantial, but have modeled this program on others that have shown morphological and functional effects in heart failure patients (11). At this exploratory stage, we feel that it is essential to use a stimulus that affects muscle size and function, with future studies modifying the NMES dose to establish a threshold that elicits a training effect with the highest subject compliance rate. Daily logs and weekly phone contacts will be used to track compliance, and compliance will be covertly monitored using the device software.

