Control patients will not receive an NMES device. We chose not to utilize a control NMES intervention (eg, stimulation below threshold to elicit contraction) to mitigate the possibility that patients may increase stimulation to produce muscle contractions if there is perceived benefit. Rigorous control over the NMES stimulus is preferable to controlling for any effects of sub-threshold, cutaneous electrical stimulation. Patients will be contacted weekly to assess their recovery and discuss issues related to general health to equate the degree of interaction with study personnel to that of the NMES intervention group.

Quality of Life measures: will be assessed with the following questionnaires which will be obtained at baseline (discharge) and 1 month following discharge

- a. Self-reported physical functioning assessment using the Medical Outcomes Study Short Form-36 (MOS SF-36) survey questionnaire (0-100 scale) with 100 representing excellent physical functioning
- b. Kansas City Cardiomyopathy questionnaire

Activities of Daily Living measures:

- a. Lawton Brody ADL questionnaire
- b. Katz Index of Independence in Activities of Daily Living

References cited above:

1. Ades, P. A., Savage, P. D., Cress, M. E., Brochu, M., Lee, N. M., and Poehlman, E. T. (2003) Resistance training on physical performance in disabled older female cardiac patients. *Med Sci Sports Exerc* **35**, 1265-1270
4. Rengo, J. L., Savage, P. D., and Ades, P. A. (in press) Directly measured physical function in cardiac rehabilitation. *J Cardiopulm Rehabil Prev*
5. Guyatt, G. H., Sullivan, M. J., Thompson, P. J., Fallen, E. L., Pugsley, S. O., Taylor, D. W., and Berman, L. B. (1985) The 6-minute walk: a new measure of exercise capacity in patients with chronic heart failure. *Can Med Assoc J* **132**, 919-923

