The PIs or the study coordinator ([name]) will monitor the safety of the research procedures/interventions for this study. [name] or [name] will be available on-site for all assessments that may pose safety concerns for volunteers. Additionally, subjects will be contacted weekly to review device use and any difficulty or issues that may have occurred since the last contact. General muscle soreness is expected in some subjects and will not be considered an adverse event. Subjects reporting severe muscle discomfort limiting daily activity or other potential adverse events (i.e. skin irritation) will be instructed to discontinue device use pending further review. In this context, study personnel will be readily available to monitor volunteer safety throughout the study. If an event occurs that affects participant safety, [name] will alert [name], who will adjudicate the event with respect to its severity, expectedness and relatedness to participation in the study. Because numerous studies in our laboratories and others have demonstrated the safety of this regimen of testing in patients from with a broad range of clinical backgrounds (eg, heart failure patients, cancer patients, advanced-stage, knee OA patients; healthy elderly), we expect minimal problems related to testing or the intervention. Considering the low risk nature of these studies, we have not incorporated "stoppage criteria" for the overall study. Instead, [name] will decide whether an individual participant should continue with the study following occurrence of any adverse events or unanticipated problems, taking into consideration what is in the best interest of each individual patient.

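### The weekly control calls match only how often patients are called after discharge, not overall staff contact, so a difference cannot be credited to stimulation alone

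*Combined protocol and SAP*

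**What the plan says.** The comparator is unblinded usual care: "Control patients will not receive an NMES device", and no sham is used. Under Procedures, Treatment phase, the control contact is described as follows: "Patients will be contacted weekly to assess their recovery and discuss issues related to general health". The stated purpose of these calls is "to equate the degree of interaction with study personnel to that of the NMES intervention group".

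The same section describes what NMES patients receive. On training: "Training in the use of the NMES device will begin prior to day of discharge", and "This training will consist of one session per day of ~15 min to familiarize the volunteer with the unit". On monitoring: "Daily logs and weekly phone contacts will be used to track compliance, and compliance will be covertly monitored using the device software". Under Randomization and blinding, an unblinded project manager trains the NMES patients and oversees them during the intervention.

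The Adverse Event and Unanticipated Problem (UAP) Reporting section describes the weekly contact without separating the arms: "subjects will be contacted weekly to review device use and any difficulty or issues that may have occurred since the last contact".

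The payment schedule lists one call in each of weeks 1 to 4 and shows no difference by arm.

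**The concern.** The plan claims a property that its own description of the two arms does not deliver in full. The claim matters because, without a sham, equal staff contact is the only control for non-specific effects that the plan states. Patients know their allocation. The primary outcome, 6-minute walk distance, depends on effort, and the KCCQ and SF-36 are self-reports. Coaching, encouragement and compliance checks could plausibly affect all three without any muscle stimulation.

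The primary aim is worded as the effect of NMES of the leg muscles, and the Treatment phase text looks ahead to studies of NMES dose. Both need the result to be attributable to the stimulus. If readers accept that contact was equated, they will attribute more to stimulation than the design allows.

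The weekly contact is also a route by which problems come to light, and the two sections describe its content differently.

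**Working it through.** **1. Contact described for each arm**

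| Element | NMES | Control | Matched? |
|---|---|---|---|
| Calls after discharge (payment schedule, weeks 1–4) | 4 | 4 | Yes |
| Described purpose of calls | Compliance and device use | Recovery and general health | No |
| Device training before discharge | About 15 min per day, days not stated | None described | No |
| Daily log | Yes | None described | No, but self-completed |
| Oversight by project manager | Stated | Not stated | Unclear; may be the same calls |

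The absence of a control log is inferred, because logs appear only in the text on NMES.

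**2. Size of the staff-time difference**

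- Calls: 4 − 4 = 0.
- Training: 15 min × k days against 0 min. The plan does not give k. Assuming k = 1 to 7, the difference is 15 × 1 = 15 min to 15 × 7 = 105 min, all of it in hospital.
- Home sessions: 5 per week × 4 weeks = 20. These are self-administered and do not count as staff contact.

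The call frequency is therefore equal, and the total interaction is not.

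**3. Agreement between the two descriptions of the calls**

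The UAP section says that subjects are called to review device use. Controls have no device, so that part can apply only to NMES patients. The Treatment phase text gives control calls a different content. No script in the protocol reconciles them.

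**4. Whether the analysis can separate the components**

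The Statistical Analysis section specifies ANCOVA of the 4-week value with the discharge value as covariate. Training and compliance calls go to one arm only, so they coincide with the treatment indicator. The treatment coefficient estimates stimulation, training and monitoring together, and covariate adjustment cannot divide them.

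**5. Whether the sample size is affected**

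The plan's figure reproduces. With a difference of 50 m, SD 60 m, two-sided 0.05 (sidedness is not stated) and 80% power:

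n per group = 2 × (1.960 + 0.842)² × 60² / 50² = 2 × 7.85 × 1.44 = 22.6, rounded up to 23.

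The exact t-test gives 78.9% power at 23 per group and 80.7% at 24, which agrees with the stated 24. Recruitment is 48 / (1 − 0.20) = 60. Nothing in this point changes these numbers.

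**The case against.** The strongest reply is that the comparator is labelled usual care, and that training and compliance tracking are part of delivering self-administered home NMES. On that reading the trial compares a programme with usual care, and unequal contact belongs to the treatment. The sham was also omitted for a different reason, the risk that patients would turn up the stimulation, and not because contact was thought to be matched. This reply stands: the programme comparison is valid. It does not rescue the sentence about equal interaction or attribution to stimulation alone.

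A reader might infer more than the documents support:

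- **That emergency visits and readmissions are recorded differently by arm.** The plan does not say that these data come from the calls. The outcome runs to 3 months, whereas the listed calls end at week 4.
- **That adverse events are asked about differently.** The UAP wording on difficulties or issues can cover both arms, and no script is shown. Different prompting is possible but not established.
- **That NMES patients get extra face-to-face time throughout the 4 weeks.** The training sessions are described before discharge only.
- **That logs and oversight are additional staff contact.** A log completed by the patient is self-monitoring, not interaction with staff. The project manager's oversight may consist of the weekly calls already counted.
- **That the bias can be stated in metres.** The documents give no estimate of a contact effect on walk distance, so any figure would be a guess.

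**Conclusion.** The point holds in a limited form. Call frequency after discharge is matched; total interaction and the described content of the calls are not. The in-hospital difference is 15 minutes per training day, or 15 to 105 minutes if training lasts an assumed 1 to 7 days. An effect of this contact would probably favour NMES, but its size cannot be obtained from the documents.

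The conclusion assumes that controls receive no training session or log, since none is described. It also assumes that compliance and device questions are confined to the NMES arm, which follows from controls having no device.

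The consequence is for attribution and for the accuracy of one stated design property. It does not invalidate the randomised comparison, the planned ANCOVA or the sample size.

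**What to change.** 1. Use one call script in both arms, with identical questions on recovery, symptoms and adverse events in the same order. Put device and compliance questions last, for NMES patients only. Align the Treatment phase and UAP Reporting sections with this script.
2. Limit the statement on equal interaction to the frequency of calls after discharge. List the contact that each arm receives, including the number of training days. Word the conclusion as the NMES programme (device, training and monitoring) versus usual care with weekly calls.

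The cost is slightly longer calls, on a schedule that already exists, and a narrower claim about mechanism. No visits or patients are added.

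A daily log for controls is not part of this recommendation. It would reduce the self-monitoring difference, but it would add self-monitoring to a usual-care arm and might make controls more active. Neither change removes the difference in pre-discharge training, which is why the conclusion has to be worded as in item 2.

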Statistical Considerations: *Delineate the precise outcomes to be measured and analyzed. Describe how these results will be measured and statistically analyzed. Delineate methods used to estimate the required number of subjects. Describe power calculations if the study involves comparisons. Perform this analysis on each of the primary and secondary objectives, if possible.*

Statistical Analysis:

Primary outcome is the 6MW. Other outcomes include SPPB, KCCQ and MOS SF-36 questionnaire results and subsequent ER visits and hospitalizations. The two experimental groups will be compared on baseline demographic characteristics using one-way Analysis of Variance (ANOVA) for continuous measures and chi-square tests (or Fisher's Exact Test) for categorical variables. Our primary outcome is to assess changes in physical function (specifically 6MW) between study groups to test whether NMES improves functional recovery from discharge to 4 weeks. We will use analysis of covariance to model primary and secondary outcomes, as this is the preferred model to assess data in pre-post RCTs. In this model, the 4-week post-discharge value is the dependent variable and the value at hospital discharge is a covariate. Sex interactions for response to NMES will be examined. We will assess QOL by questionnaires to determine if NMES improves patient-reported QOL vs. usual care. Clinical and other factors that may modify the response to NMES (eg, length of stay, etc) can be included in the model to control for potential confounders that might differ by group in the event that randomization fails to equate groups.

Sample Size Calculation:

The proposed sample of 60 participants is based on having sufficient power to calculate differences in our primary outcome (6MW) between the control condition and the intervention and accommodating for potential drop outs (20%) from the study.¹¹ Power is estimated to be 80% to detect a difference in the change in 6MW between the 2 groups at the $p<0.05$ level. These estimates are based on data from a meta-analysis of RCTs of NMES in *stable* patients with chronic heart failure which detected a difference of 47 m between NMES group vs placebo as well as our pilot data of CABG patients, where patients randomized to NMES increased 6-MW distance 73 m further than controls.¹¹ We assume a 6-MW distance of 250 ± 60 m (mean \pm SD) at hospital discharge in both groups. Additionally, we have reduced the improvement in 6-MW distance in the NMES group by ~30% to 50 m (6-week post-discharge NMES: 250 ± 60 m vs. Control: 300 ± 60 m) to be conservative. This magnitude improvement in 6-MW is similar to meaningful changes found in 6-MW performance in older adults with mild- to moderate mobility disability undergoing home-based strength training (47 m) and is twice the minimal clinically significant difference in patients with cardiac disease following CR (25 m).¹⁸ Therefore, we will need to recruit 60 patients with our target of 48 patients to complete the study (n=24/group), assuming a drop out of 20%. We have not performed sample size estimates for SPPB or secondary outcomes, as extrapolating the ability of NMES to affect other variables is challenging barring relevant preliminary data, particularly in *recently hospitalized* heart failure patients.

Risks/Benefits: Describe any potential or known risks. This includes physical, psychological, social, legal or other risks. Estimate the probability that given risk may occur, its severity and potential reversibility. If the study involves a placebo or washout period, the risks related to these must be addressed in both the protocol and consent. Describe the planned procedures for protecting against or minimizing potential risks and assess their likely effectiveness. Where appropriate, discuss plans for ensuring necessary medical or professional intervention in the event of adverse effects to the subjects. Discuss the potential benefits of the research to the subjects and others. Discuss why the risks to the subjects are reasonable in relation to the anticipated benefits to subjects and others. Discuss the importance of the knowledge gained or to be gained as a result of the proposed research and why the risks are reasonable in relation to the knowledge that reasonably may result. If there are no benefits state so.

Potential risks: Below we have highlighted those procedures/measurements that have anything greater than negligible risk to the volunteers' health for each phase of the study.

Testing: Risks associated with functional testing are minimal. All of the activities are similar to those performed during the conduct of normal daily activities. If volunteers are unable to do any of the activities because of limitations of their heart condition, they will not be required to perform them and testing will be monitored by trained personnel.

NMES intervention: NMES is a generally safe procedure, delivered in the proposed study by an FDA approved device. Although evidence is limited, some have suggested that NMES could increase the risk of DVT, which may have serious health consequences. However, several published reports show that NMES significantly reduces the risk of developing deep vein thromboses (DVT) (1) and we will actively exclude any individual with a known coagulopathy. Because of the location of the stimulating electrodes (upper leg), the risk of NMES dislodging a DVT is likely minimal. We will also exclude any volunteers that currently have an implanted cardiac defibrillator or pacemaker, as this is contraindicated for NMES use (1). Patients may experience some painful muscle contractions as they first adjust the stimulus to a tolerable level, which can be quickly corrected by reducing the stimulation intensity. After treatment, muscles soreness may occur. The level of fatigue and/or soreness, however, will be similar to that which occurs following a standard exercise training session and should dissipate over time as the volunteer's muscles become accustomed to the electrically-stimulated contractions (ie, they become trained).

Benefits: The direct benefit of the research to volunteers is minimal. NMES may improve skeletal muscle structure or function and, in turn, improve physical functional capacity. Because of this, patients may experience improved physiological capacity, which could reduce disability. If we find that NMES has beneficial effects on physical function, further research and application of the technique to heart failure patients may assist in the development of more effective transitional rehabilitative care approaches to mitigate long-term functional morbidity.

References cited above:

1. Houghton, P. E., Nussbaum, E. L., and Hoens, A. M. (2010) Electophysical agents. Contraindications and precautions: an evidence-based approach to clinical decision making in physical therapy. *Physiother Can* **62**, 1-80

Therapeutic Alternatives: List the therapeutic alternatives that are reasonably available that may be of benefit to the potential subject and include in the consent form as well.

Not Applicable

There are no alternative rehabilitation regimens during the early, post-hospitalization period for heart failure patients.

Data Safety and Monitoring: The specific design of a Data and Safety Monitoring Plan (DSMP) for a protocol may vary extensively depending on the potential risks, size, and complexity of the research study. For a minimal risk study, a DSMP could be as simple as a description of the Principal Investigator's plan for monitoring the data and performance of safety reviews or it could be as complex as the initiation of an external, independent Data Safety and Monitoring Board (DSMB). The UVM/UVM Medical Center process for review of adverse events should be included in the DSMP.

Drs. [name] and [name] will monitor the safety of the research procedures for this study. We have not set up a formal safety committee for several reasons. First, the PIs and the investigative team have a long history of performing the measurements proposed in this proposal. The procedures carry relatively low risk to the volunteers. Second, because of the small number of patients and track record of performing these procedures, it is highly unlikely that we will need to "stop" the study or significantly

alter the procedures. If any problems/unanticipated events arise related to the NMES intervention, [name] will determine the nature of the problem and its relatedness to the NMES intervention and decide whether continued participation in the study is in the best interest of the patient. As detailed above, however, NMES is FDA-approved for this indication and we have taken precautions to minimize the potential for adverse effects.

Adverse Event and Unanticipated Problem (UAP) Reporting: *Describe how events and UAPs will be evaluated and reported to the IRB. All protocols should specify that, in the absence of more stringent reporting requirements, the guidelines established in the Committees on Human Research "Adverse Event and Unanticipated Problems Reporting Policy" will be followed. The UVM/UVM Medical Center process for review of adverse events and UAPs to subjects or others should be included in the DSMP.*

The PIs or the study coordinator ([name]) will monitor the safety of the research procedures/interventions for this study. [name] or [name] will be available on-site for all assessments that may pose safety concerns for volunteers. Additionally, subjects will be contacted weekly to review device use and any difficulty or issues that may have occurred since the last contact. General muscle soreness is expected in some subjects and will not be considered an adverse event. Subjects reporting severe muscle discomfort limiting daily activity or other potential adverse events (i.e. skin irritation) will be instructed to discontinue device use pending further review. In this context, study personnel will be readily available to monitor volunteer safety throughout the study. If an event occurs that affects participant safety, [name] will alert [name], who will adjudicate the event with respect to its severity, expectedness and relatedness to participation in the study. Because numerous studies in our laboratories and others have demonstrated the safety of this regimen of testing in patients from with a broad range of clinical backgrounds (eg, heart failure patients, cancer patients, advanced-stage, knee OA patients; healthy elderly), we expect minimal problems related to testing or the intervention. Considering the low risk nature of these studies, we have not incorporated "stoppage criteria" for the overall study. Instead, [name] will decide whether an individual participant should continue with the study following occurrence of any adverse events or unanticipated problems, taking into consideration what is in the best interest of each individual patient.

Adverse events will be reported by one of 3 mechanisms. First, the joint University of Vermont/University of Vermont Medical Center (UVMMC) Committee for Human Subject Research Adverse Event Reporting Document. These reports will be sent to the office of the Committee for Human Research in the Medical Science (CHRMS) within 2 days of the event. Reporting any adverse events will be the responsibility of the PIs. The CHRMS will make a determination as to whether additional reporting requirements are indicated. Additionally, the UVMMC Patient Safety Reporting system (SAFE), which may be initiated by health care center staff or study personnel. These forms will be forwarded within 3 days to the PI, UVMMC Risk Management Office, CHRMS and other appropriate agencies, as indicated by the nature of the report. Reviews of protocol specific adverse events will be performed no less than annually. Additionally, any adverse event that occurs will be forwarded to the PIs for reporting to the Human Subject Research Protection Office within 1 week of occurrence. Of note, these protections against risk include both physical risks to the volunteers, as well as risks associated with any breach in confidentiality.

On an annual basis, Drs. [name] and [name] will assess data being gathered and safety of volunteers to assess the pattern or frequency of events to identify occurrence of any event or problem that alters the safety profile of the procedures being performed. The exception would be occurrence of a serious adverse event or unanticipated problem that necessitates re-evaluation of the expected risk of the study procedures at an earlier time point. Additionally, they will evaluate data collection and storage to ensure the confidentiality of data and quality. Each of these evaluations will be followed by reports of study progress and patient safety to the University of Vermont CHRMS via yearly progress reports.

Withdrawal Procedures: *Define the precise criteria for withdrawing subjects from the study. Include a description of study requirements for when a subject withdraws him or herself from the study (if applicable).*

Volunteers will be withdrawn if the research team, clinician and/or safety officer feels that further participation in the study or performance of any procedure associated with this study would, in any way, put the volunteer at undue risk or not be in their best interest. Moreover, volunteers may be withdrawn if s/he fails to attend scheduled visits or do not comply with instructions from research staff.

Sources of Materials: Identify sources of research material obtained from individually identifiable human subjects in the form of specimens, records or data. Indicate whether the material or data will be obtained specifically for research purposes or whether use will be made of existing specimens, records or data.

An individual research record will be kept on each volunteer in compliance with HIPAA standards. This record will contain identifying data, demographic information and results from all clinical research measurements and evaluations. The results of all testing will be kept confidential. All materials gathered in conjunction with the proposed studies will be used for research purposes only and will be available only to research personnel working on these studies, who have obtained proper training in human subjects research and privacy protection.

DRUG AND DEVICE INFORMATION

Investigators are encouraged to consult the UVM Medical Center Investigational Pharmacy Drug Service ([name]) prior to finalizing study drug/substance procedures.

Drug (s)

Not applicable

Drug name – generic followed by brand name and common abbreviations. Availability – Source and pharmacology; vial or product sizes and supplier. If a placebo will be used, identify its contents and source. (attach investigational drug brochure)

Preparation: Reconstitution instructions; preparation of a sterile product, compounded dosage form; mixing guidelines, including fluid and volume required. Identify who will prepare.

Storage and stability – for both intact and mixed products.

Administration – Describe acceptable routes and methods of administration and any associated risks of administration.

Toxicity – Accurate but concise listings of major toxicities. Rare toxicities, which may be severe, should be included by indicated incidence. Also adverse interactions with other drugs used in the protocol regimen as well as specific foods should be noted. Address significant drug or drug/food interactions in the consent form as well. List all with above details.

Is it FDA approved: (include FDA IND Number)

1. in the dosage form specified? If no, provide justification for proposed use and source of the study drug in that form.

2. for the route of administration specified? If no, provide justification for route and describe the method to accomplish.

3. for the intended action?

Device (s)

Not applicable

Device name and indications (attach investigational device brochure)

The interventional device used in this study: EMPI Continuum complete electrotherapy system has received FDA approval (501K: K093324) for retarding disuse-related atrophy, which we believe is one of the primary mechanisms whereby HFrEF patients become more functional disabled in the early, post-hospitalization period. That is, muscle disuse secondary to limited range of motion and muscle weakness causes skeletal muscle fiber atrophy and weakness, as well as mitochondrial rarefaction and dysfunction that further impair physical fitness.

Is it FDA approved: (include FDA IDE Number)

1. for indication specified? If no, provide justification for proposed use and source of the device.

Yes. It is approved to mitigate muscle atrophy/dysfunction associated with muscle disuse (501K: K093324) (see Appendix 3).

Risk assessment (non-significant/significant risk) - PI or sponsor needs to assess risk of a device based upon the use of the device with human subjects in a research environment.

The device (and similar devices) has been used extensively in the orthopedic and neural rehabilitation settings by physical and occupational therapists and in numerous disease states (heart failure, chronic obstructive pulmonary disease, knee replacement) to improve muscle size and function in clinical trial settings. Thus, NMES is generally a safe modality, with a long safety record. Although evidence is limited, some have suggested that NMES could increase the risk of dislodging a DVT because of the rhythmic muscle contractions induced by the electrical stimulation. However, several published reports show that NMES significantly reduces the risk of developing DVTs. In fact, the device we are using is

